## Study Tasks:

Medical History: The presence of diabetes will be determined based on American Diabetes Association criteria. This will include: duration and type of diabetes, type of diabetes medication (insulin, oral, combination therapy, diet), previous history of foot ulcers, amputation (toe, foot), lower extremity bypass, lower extremity angioplasty, Coronary artery bypass surgery, cardiac angioplasty, arthritis, liver disease, osteoporosis, malignancy, and bone tumors. We will measure height and weight to determine body mass index (BMI). We will evaluate glycated hemoglobin, albumin and prealbumin at baseline. We will confirm PAD by measuring ABI.

Social Factors: We will evaluate the following factors: marital status, years of education, type of work, tobacco history (pack years, current smoker, current use of chewing tobacco, previous smoker, no tobacco history), drug history (current, previous history, or no history), and alcohol history.

BEST Therapy: The participant will be given an active Tennant Biomodulator PRO ® by the research staff. They will place the pads on the plantar area of the foot and provide therapy for one hour. At the end of the visit, the research staff will provide an active or sham Tennant Biomodulator ® to the participant for in-home therapy. The participant will have the ability of increasing/decreasing the intensity of the therapy with the Tennant Biomodulator ®. At each visit, the research staff will provide AA batteries to the participant for the device.

Peripheral Neuropathy: Neuropathy and its severity will be assessed using vibratory perception threshold (VPT) at the affected side. VPT will be evaluated at the distal great toe and fifth metatarsal head using a Biothesiometer.

Vascular Assessment: We will assess perfusion of the macro-circulation with arterial Doppler studies and microcirculation with Skin Perfusion Pressure measurements (SPP) at the affected side. We will use the SensiLase system (Väsamed) to measure SPP in mmHg. Ankle Brachial Index (ABI) will be also measured in the case of compressive vessel and if it was feasible (e.g. in non-hemodialysis patients) on the affected side. Additionally, we will use HyperView Imaging (HyperMed Imaging, Inc., TN, USA) or Kent Camera (Kent Imaging Inc., Calgary Canada) for surface tissue oximetry measurement.

Gram Stain: Bacteria levels will be assessed by collecting a samples and ordering a Gram Stain assessment, which provides an estimate of number of bacteria in the wound. A sample will be collecting before treatment and at 4 weeks.

Wound photo: A digital photo/video will be taken to record wound size.

Thermal Image: A Thermal camera will be used to obtain an image of the wound and observe inflammation.

Definition of Healed Wounds: A wound will be considered “healed” when it is fully epithelialized with no drainage. Only patients with non-infected wound will be recruited. *Infection* will be defined as a patient with three of six clinical signs of infection (erythema, heat, edema, pain, loss of function, purulence) or leukocytosis. We will use the Infectious Diseases Society of America’s Diabetic Foot Infection guidelines to stratify the severity of infection. This guideline stratifies infections into four categories (none, mild, moderate, and severe) based on practical clinical and laboratory findings. Our group has shown this system to be predictive of morbidity.

Health Questionnaires: Quality of Life, Frailty Status, Fear of Falling, Sleep Quality, Depression and Mental Status and Device Acceptability: To evaluate functional status we will use well-accepted questionnaires, PROMIS for Quality of Life, Sleep Quality questionnaire (PSQI), MOCA for cognitive assessment, FES-I for fear of falling, CES-D for depression and TSFI for frailty status. During the last visit, we will ask an acceptability questionnaire.

Upper Extremity Assessment: Investigators will measure the participant's arm motion using a wearable sensor (LegSys, Biosensics LLC, MA USA). This sensor will be placed around the wrist. While being at a comfortable position, the participant will be asked to flex and extend their arm for 20 seconds at a fast speed. They will also be asked to repeat this task but counting backwards as the participants flex and extend their arm (dual task). (Measurement will be done at baseline and visit 4)

Heart Rate Monitoring: A comfortable chest worn sensor (BioStamp RC, MC10) will be used to measure physiological signs such as heart rate, skin temperature, and physical activity. This device will be comfortably placed on the chest attached either with two sticky electrodes or with elastic strap. Researchers will attach this device on the participant for the duration of the visit or during 24 hours. We will be assessing heart rate variability (HRV) as a surrogate of pain to determine magnitude of pain during dressing change and debridement process according to the protocol describe in Razjouyan et al (2017).

Phone Interview: Research staff will be contacting the subject to record any adverse events such as hospitalizations, ulceration falls and others.

**Optional assessments** – These may occur at any visit. However, they do not need to be performed.

Physical Exam: If they are able to stand and walk, the research staff will place 5 sensors named Legsys and Balanses (one on lower back, two on each upper thigh, and two on each shin) attached with elastic straps to test balance and record walking patterns. Research staff will ensure that the straps are not too tight to avoid poor circulation.

Physical activity: The research staff will provide the participant with a small sensor (Pamsys, Biosensics LLC, MA, USA) that will be measuring physical activity for 48 hours. It will record number of steps taken, duration of sitting, standing, walking, and lying. It will also record the number of transitions made from sitting to standing and vice versa. Researchers will provide a pre-paid envelope where the participants may use to return the device.

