**Table I: Patient Population**

Inclusion Criteria	
Able to provide informed consent
 
18-85 years old
 
Clinically confirmed diabetes (ADA criteria)
 
One or more active non-infected lower extremities ulcer or wound
 
Subject or responsible caregiver is willing and to maintain the required offloading (as applicable the location of the ulcer) and applicable dressing changes and electrical stimulation application.

Exclusion Criteria	
Subject has a demand-type cardiac pacemaker, implanted defibrillator or other implanted electronic device
 
Is pregnant
 
Is nursing or actively lactating
 
Has history of seizures.
 
Active wound infection
 
Active Charcot Foot
 
Non-ambulatory (Unable to walk 40 feet with or without assistive device)
 
Bilateral AK/BK amputation
 
Active drug/alcohol abuse (or history in the last year)
 
Dementia or severe cognitive impairment
 
Subjects with excessive lymphedema
 
Subjects with osteomyelitis and/or gangrene
 
Unable to comply with research appointments (e.g. long travel)

	
Wide spread malignancy or systemically immunocompromising disease
 
Subject has a history of or any intercurrent illnesses or conditions that would compromise the safety of the subject according to judgement of a qualified wound specialist.

--	--

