## Study Design

We are proposing a clinical study at the Baylor College of Medicine, Division of Vascular Surgery and Endovascular Therapy, to test the efficacy of daily home use of a novel electrical stimulation platform named the Tennant Biomodulator designed by AVAZZIA to accelerate wound healing, relieve pain and improve mobility in people with diabetes and non-infected plantar ulcers or wounds. In addition, we will examine immediate benefit of electrical stimulation provided by the Tennant Biomodulator on increasing skin perfusion. Our specific aims are:

**Aim1: Examine immediate benefit of lower extremity electrical stimulation to improve tissue perfusion (short term benefit):** We will recruit 40 eligible subjects (see table I for eligibility criteria). They will receive lower extremity electrical stimulation (at the shin level) for duration of approximately one hour using the Tennant Biomodulator Pro device. Skin perfusion before, at mid-point (approximately 30 min) and at the end of therapy will be measured. Skin perfusion will be assessed by Skin Perfusion Pressure (Sensilase, Vasamed Inc, MN, USA) and Kent Imaging. Other modalities such as HyperView Imaging (HyperMed Imaging, Inc., TN, USA) may be also used as comparator. Our hypothesis is:

*H1:* One-hour use of lower extremity electrical stimulation therapy will increase tissue perfusion.

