**Randomization & Blinding**

This study will be designed as a double-blind randomized clinical model. Both patients and the treating podiatrist will be blinded. The study coordinator will be aware of the assignment (active device or sham device) by a guide provided by the sponsor. The guide will identify which devices are active or inactive.

The control group will receive an identical device but without active electrical stimulation output. The physician treating the wound as well as patients will be blinded to the type of device. Only the study coordinator will be aware of assignment (active device or sham device). The study coordinator will reveal the group to the participant during the last visit. At that time, the coordinator will ask the participant if they would like to continue with the therapy. If they agree, participants will be instructed to contact Avazzia Inc. to receive a device after the completion of the study phone interview (12 weeks).

Each unit will be coded with a unique identification number, and the study coordinator will reveal their status, placebo or electric stimulation, only at the end of data collection from the last patient. The PI and data analyzer will be able to match the status of the identification numbers with the corresponding units to analyze the data. Since participating patients will have moderate-to-severe peripheral sensory neuropathy, they will be unable to determine via “feeling” whether or not they were receiving electrical stimulation. Furthermore, the credibility of design is enhanced due to all enrolled patients being therapeutically naïve to the sensation of electrical stimulation.

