### **Schedule of Events**

Visit	Baseline assessment	Follow up					
		#	0	1	2	3	4
Consent & HIPPA forms	X						
Screening (inclusion and exclusion criteria)	X						
Medical & Surgical History	X						
Gram Stain	X					X	
Neuropathy assessment (VPT)	X		X			X	
Immediate Skin Perfusion Pressure Response after one hour of BEST Therapy	X						
BEST Therapy	X	X	X	X	X		
Optional assessments		X				X	
Upper Extremity Test	X					X	
WiFi wound classification	X	X	X	X	X		
Vascular Assessments (SPP and HyperView/Kent Imaging)	X					X	
Wound Photos	X	X	X	X	X		
Thermal Images	X		X			X	
Wound Care (standard of care)	X		X			X	
Adverse Events Reporting	X	X	X	X	X		
Pain Questionnaire (VAS)	X	X	X	X	X		
Heart Rate Variability	X	X				X	
Health Questionnaires (MOCA, FESI, CES-D, PSQI, TSFI, Promis Global)	X					X	
Device Acceptability Questionnaire						X	
Phone Interview							X

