### **Subject compensation:**

Participants will be compensated with \$50 per visit. For five completed visits a total of \$250 may be compensated to the subject. We will be also providing parking validations.

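### Both stated reasons why participants cannot feel which device they have are unsecured by the plan: all, sham arm included, first get an active clinic hour, neuropathy is not an entry criterion, and no check of the blind is planned.

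*Protocol*

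**What the plan says.** **The active clinic hour.** Study Design, Aim 1, recruits 40 subjects: "They will receive lower extremity electrical stimulation (at the shin level) for duration of approximately one hour using the Tennant Biomodulator Pro device". The Schedule of Events lists at baseline "Immediate Skin Perfusion Pressure Response after one hour of BEST Therapy". Study Tasks (BEST Therapy) says "The participant will be given an active Tennant Biomodulator PRO", with no split by arm, and then: "At the end of the visit, the research staff will provide an active or sham Tennant Biomodulator".

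**Why participants are said to be unable to tell.** Randomization & Blinding gives two grounds. The first is neuropathy: "Since participating patients will have moderate-to-severe peripheral sensory neuropathy, they will be unable to determine via" feeling which device they have (Aim 2 says the same). The second is that "the credibility of design is enhanced due to all enrolled patients being therapeutically" naive to the sensation. Separately, the active and sham home units are identical and carry coded identification numbers.

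**Eligibility.** Besides consent, age, diabetes and willingness to follow the regimen, Table I asks for "One or more active non-infected lower extremities ulcer or wound". It sets no neuropathy or vibration perception threshold (VPT) criterion and does not exclude earlier electrical stimulation. VPT is only an assessment and outcome.

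**Checking the blind.** The Schedule of Events, Study Tasks, the protocol's Statistical analysis section and the SAP contain no treatment-guess item or blinding index. The nearest item is a last-visit acceptability questionnaire whose content is not described.

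**The concern.** A sham participant who felt the clinic session has a reference against which a silent home unit may be recognised. Such a participant may expect no benefit, and that can shift any outcome that depends on what the participant perceives or reports. Those outcomes are VPT, which measures one of the two primary outcomes, and pain, sleep and quality of life. Pain is the first hypothesis under Purpose, although Aim 2 lists it as secondary. Wound size from photographs is less exposed.

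Without a check, nobody could say afterwards whether the blind held. The Sample size section says the trial is meant to estimate a trend and to size a follow-up study, so any bias in these outcomes would carry into that estimate.

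**Working it through.** The plan gives no figure for the blind, so there is none to reproduce. The main check is textual.

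**1. Does the active hour reach the sham arm?** Aim 1 stimulates 40 subjects; Aim 2 randomises 20 + 20 = 40; the Sample size section gives a study total of 40. The two aims therefore share the same people. The BEST Therapy paragraph shows the order directly: active clinic unit first, allocated home unit at the end of the visit. So every sham participant has at least one active hour before home use.

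**2. Does the naivety ground survive?** Participants may be naive at enrolment, although Table I does not require it. They are not naive at the first home session. The clinic and home units are different models, but Study Device gives them the same output specifications.

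**3. Does the neuropathy ground survive?** It is asserted, and no entry criterion secures it. Other text allows for sensation: the risks section covers tingling that is too intense, and Study Tasks lets the participant adjust the intensity at home.

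**4. How much active exposure does the sham arm get?** The one-hour perfusion response is marked at baseline only. A separate BEST Therapy row carries five marks, and Subject compensation refers to five visits ("For five completed visits a total of" $250). Home use is at most 28 one-hour sessions.
- One clinic session: active arm up to 28 + 1 = 29 h, sham arm 1 h (1/29 = 3.4%).
- Five clinic sessions, added to home use: up to 28 + 5 = 33 h against 5 h (5/33 = 15.2%).

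The documents do not settle which applies. The extracted table is broken, so the number of marks can be read but their column positions are not safe.

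**5. How large could the bias be?** All inputs are assumptions, not taken from the documents: 10% to 50% of the sham arm recognise the silent unit, and expectation is worth 0.1 to 0.5 SD. Bias = share × expectation. With no true effect, a two-sided 5% t-test rejects with probability P(|T| > critical value), where T is noncentral t with noncentrality bias × √(n/2).

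| Case | Bias (SD) | 20 v 20 | 18 v 18 |
|---|---|---|---|
| Low | 0.1 × 0.1 = 0.01 | 5.0% | 5.0% |
| Mid-range | 0.3 × 0.3 = 0.09 | 5.9% | 5.8% |
| Extreme | 0.5 × 0.5 = 0.25 | 12.0% | 11.3% |

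For example, the extreme case at 20 v 20 has noncentrality 0.25 × √10 = 0.79.

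**6. What could a treatment-guess item detect?** Exact two-sided binomial test against 50%, with a true correct-guess rate of 70% (assumed):
- 20 in one arm (reject at ≤5 or ≥15): power 42%.
- 40 pooled (reject at ≤13 or ≥27): power 70%.
- 36 pooled, after 10% drop-out (reject at ≤11 or ≥25): power 61%.

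With 20 in one arm, power is 80% at a true rate of 80% and 99% at 90%.

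**The case against.** **Appearance is protected.** The identical, coded units are a real part of the blind and nothing here undermines them. Many participants may have neuropathy in practice. The clinic unit is a different model, which may weaken the cue. All of this stands. A reader might infer that the blind fails; the documents do not show that. Only the two grounds about feeling are affected.

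**The sensation text is conditional.** The risks section describes what could happen, and Study Tasks only says that intensity can be changed. A reader might infer that the protocol expects participants to feel the device. It allows for this without predicting it.

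**Weekly active sessions are not established.** The BEST Therapy paragraph describes a single handover and mentions only batteries at each visit, so the five-mark row could mean ongoing allocated therapy. This stands, and the count is a matter to reconcile.

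**The bias figures multiply one assumption by another.** True. The mid-range effect is small, and active hours given to the sham arm could pull the other way by diluting the contrast. The case rests on the text.

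**Later reveal brings little.** The 12-week call records adverse events and the SAP specifies no 12-week analysis, so the gain would be small.

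**Aim 1 sample size.** A reader who pictures the baseline hour as a two-arm comparison might infer that the 27 subjects must be per group. The Sample size section describes a comparison with baseline. An exact two-sided McNemar test of 50% v 10%, assuming independent responses, has 85.7% power with 27 subjects in total, so that inference is not supported.

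**Conclusion.** The plan is wrong as written on one specific matter: it relies on naivety and neuropathy to show that participants cannot feel which device they have. Its own baseline session ends the first, and its entry criteria do not secure the second. It also plans no check. These conclusions follow from the text and need no assumption.

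Whether unblinding occurs, and how much it matters, is unknown. The 5.0% to 12.0% range at 20 v 20 depends wholly on the assumed recognition and expectation values, and the mid-range 5.9% is a modest departure from 5%. The exposure is concentrated in VPT and the self-reported outcomes. This should be fixed because correction is cheap and, without it, results on those outcomes cannot be defended against an expectation effect.

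**What to change.** 1. **Correct the two statements** in Aim 2 and Randomization & Blinding: participants may have neuropathy, and may be naive at enrolment but not after the baseline session. Do not cite either as protecting the blind. Cost: wording only.

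2. **Add a treatment-guess item** to the last-visit acceptability questionnaire, asked before any reveal. Report it by arm, pooled and by baseline VPT, and interpret VPT and the self-reported outcomes in its light. Cost: one question. Its power is limited, so a non-significant result would not prove that the blind held; a correct guess may also reflect perceived benefit. If participants have already been told their group, the item cannot be recovered and the limitation should be reported instead.

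3. **Reconcile the reveal wording.** Aim 2 and one part of Randomization & Blinding reveal the group at each participant's last visit. A later sentence in the same section places the reveal after the last patient's data collection. The later sentence may concern the principal investigator and analyst; if so, say so. Holding the participant's reveal until after the 12-week call is optional and of small benefit.

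4. **Reconcile the therapy description**: whether the five-mark BEST Therapy row means one active clinic session or several, and whether stimulation is at the shin (Aim 1) or the plantar foot (Study Tasks).

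5. **Reconcile the sham arm's active baseline hour with the blinding rationale.** Moving or replacing that session would change the Aim 1 question or cost it power. That is the sponsor's design trade-off, and no particular arrangement is prescribed here.

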**Aim2: Examine long-term benefit of daily home use of lower electrical stimulation (long-term benefit):** Eligible participants will be randomized (ratio: 1:1) to either active (active group, n=20) or sham (sham group, n=20) therapy group. After receiving education, both groups will receive a home-based electrical stimulation system (Tennant Biomodulator device) for daily use at home up to 4 weeks. The duration of each treatment session per day will be one hour. The active group will receive an active electrical stimulation device. The control group will receive an identical device but without active electrical stimulation output. Participants and physicians who are treating the wound would be blinded to the type of device assignment. The study coordinator will be aware of assignment (active device or sham device). Each unit will be coded with a unique identification number. At the last visit, the study coordinator will reveal their group allocation. Since participating patients will have moderate-to-severe peripheral sensory neuropathy, they will be unable to determine via “feeling” whether or not they were receiving electrical stimulation. Patients will visit the clinic on weekly basis up to 4 weeks for assessing outcomes. The primary outcomes include changes in speed of wound healing and changes in plantar sensation. Secondary outcomes include patients self-report outcomes (e.g., pain, sleep quality, and quality of life), changes in mobility (e.g. physical activities and gait), and adverse outcomes (e.g., infection, amputation, etc.). Skin perfusion will be assessed similar to the method described in the Aim 1. Plantar sensation will be assessed using vibratory

perception threshold. Balance will be assessed using wearable sensors (BalanSENS, Biosensics LLC, MA, USA), mobility will be assessed using wearable sensors (PAMSys, Biosensics LLC, MA, USA), sleep quality will be assessed using PSQI questionnaire, and quality of life will be assessed using PROMIS Global.

Our hypotheses are

*H2:* Weekly speed of wound healing would be higher in the active group compared to the shame group

*H3:* Plantar sensation is improving in the active group in response to active therapy.

*H4:* Patient-reported outcomes and other secondary outcomes will be improved in the active group.

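### As scheduled, the optional 48-hour activity recording has no untreated baseline, and its final window opens at the visit where participants are told their arm

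*Protocol*

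**What the plan says.** **The measure.** Study Design, Aim 2, lists mobility, including physical activity, among the secondary outcomes and names PAMSys as the instrument. Study Tasks describes a small sensor "that will be measuring physical activity for 48 hours". On its return: "Researchers will provide a pre-paid envelope where the participants may use to return the device". It belongs to the optional assessments, of which the protocol says: "These may occur at any visit. However, they do not need to be performed".

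**The schedule.** The Schedule of Events gives the row "Optional assessments" two marks. The second stands in the same column as the last mark of the Upper Extremity Test, and Study Tasks fixes that test's timing: "Measurement will be done at baseline and visit 4".

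**Start of therapy.** Under BEST Therapy, the participant has an hour on an active PRO device in clinic, with no split by arm. Then: "At the end of the visit, the research staff will provide an active or sham Tennant Biomodulator". Home use is daily, one hour a session, for at most four weeks.

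**End of therapy and reveal.** Study Design states: "At the last visit, the study coordinator will reveal their group allocation". Randomization & Blinding repeats this. For those who wish to continue, it adds: "participants will be instructed to contact Avazzia Inc. to receive a device after the completion of the study phone interview (12 weeks". A later sentence in that section holds back the status of the units until the final participant's data have been gathered, without saying from whom.

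**Analysis.** The SAP assesses outcome changes against baseline, within and between groups, with a mixed model or GEE.

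**The concern.** A change-from-baseline analysis of a masked home therapy needs a first measurement before treatment and a last one while treatment and masking are still in place. A 48-hour recording that begins when a sensor is handed out looks forward from the visit, not back. At the first visit it therefore looks into the treatment period, and at the last visit it looks past the end of treatment and past the reveal.

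Step counts and walking time are behaviours. A participant who has just learned that the device was inactive, or active, may move differently for that reason alone. If the change score is read as the effect of four weeks of masked stimulation, it may credit the device with a response to the disclosure, or miss an effect that was already present in the first recording or had faded by the last. Neither fault can be repaired by modelling once the data are in.

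**Working it through.** No sample size or power figure is involved, so there is nothing to reproduce. The check places the 48-hour window on the visit sequence.

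**1. The recording follows the visit.** It lasts 48 hours and the sensor can be posted back, so nearly all of it takes place away from clinic. The start time, and the order relative to the clinic session, are not stated.

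**2. It cannot precede the baseline visit.** The Schedule marks consent at baseline, and the Informed Consent section requires it before any study procedure.

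**3. First recording, two readings of the broken table.**
- *Visit 0.* The clinic session and the hand-over of the home device happen that day. The 48 hours contain about 1 to 3 home sessions, depending on whether home use starts the same day (not stated). That is 1/48 = 2.1% to 3/48 = 6.3% of the window. If waking time is assumed to be 16 hours a day, it is 1/32 = 3.1% to 3/32 = 9.4% of waking hours. Participants are told to sit or lie during sessions.
- *Visit 1.* Visits are weekly, so the window follows about one week of home therapy.

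Neither reading gives an untreated 48 hours.

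**4. Final recording.** The second mark aligns with visit 4. The participant is told the arm at that visit, so at most the hours of the visit itself are masked. Home therapy runs for at most four weeks, and continuation devices come only after the 12-week interview. If therapy stops at four weeks, the window contains 0 home sessions.

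**5. What the change score then estimates.** Write *E* for the between-arm effect on activity late in four weeks of masked therapy, *e1* for the effect already present in the first recording, *r* for what remains after stopping, and *u* for the effect of knowing the arm. Then:

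between-arm difference in change = (*r* + *u*) − *e1*

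This equals *E* only if *r* + *u* − *e1* = *E*, which nothing in the plan secures. A masked recording made in week 4 and compared directly between randomized arms targets *E*, with no *e1* to subtract and no *u* to add.

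**6. Which comparison is hit.** No split by arm is described for the clinic session, and seated home sessions occur in both arms, so these mainly disturb within-group change. Early exposure to an active rather than a sham home device, the loss of treatment and the reveal can all disturb the between-arm comparison.

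**The case against.** The strongest reply is that the protocol does not fix a wrong time. The assessment is optional and allowed at any visit, so a sensor handed out at visit 3 is already permitted. That is true, and a reader should not infer that a recording follows every visit. It does not rescue the plan: the two marks in the schedule are the only direction staff have, and the second leads to visit 4.

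Other limits also stand:
- No passage defines a baseline activity recording, and the first mark cannot be settled between visit 0 and visit 1. A reader might infer that it certainly covers the first two days of therapy; the documents do not establish that. Both readings are on treatment, so the conclusion holds either way.
- That therapy has ended by the final window is inferred. Return of the home device at visit 4 is not stated.
- The sentence delaying disclosure to the end of data collection conflicts with the last-visit reveal if it covers participants. It is followed by investigator and analyst access and may concern only them. If participants were in fact told later, the masking part of this point would fall and the baseline part would stand.
- The SAP's change-from-baseline sentence is generic and does not mention activity. Mobility is a secondary outcome, also covered by gait measures (themselves optional), and the protocol concedes that the sample may not suffice for every outcome.

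**Conclusion.** The point holds for PAMSys activity as scheduled. No recording can serve as an untreated baseline. One begun at visit 4 is unmasked, on the two passages that place the reveal there, and off home therapy by inference from the four-week limit and the 12-week device rule.

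The bias cannot be sized, and its direction is open. A reader might want to state the share of the effect that is lost. That needs *e1*, *r* and *u*, and the documents give none of them, so any percentage would only restate what was assumed. A reader might also extend the point to the 24-hour chest sensor. Its stated purpose is pain during dressing change and debridement, and no endpoint is defined on the hours after the visit, so the same fault is not shown there. Nor does the point discredit mobility as a whole; it concerns this one optional measure.

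The change should be made because it is cheap and the fault is irreparable after data collection, but it does not touch the primary outcomes.

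**What to change.** - Issue the final sensor at visit 3, record 48 hours in week 4, and collect it at visit 4 before any reveal. With weekly visits the recording takes 2 of the 7 days between visits 3 and 4; state which two, preferably those just before visit 4.
- Do not treat the first recording as an untreated baseline. Compare the arms directly on the visit-3 recording, adjusted for pre-treatment covariates already collected, such as age and BMI, which the protocol's analysis section already names. Do not adjust for the first recording, since it may already carry part of the effect.
- State in the protocol which visits issue the sensor and when the 48 hours start relative to the clinic session. Put the direct comparison in the SAP for this measure.
- Reconcile the last-visit reveal with the sentence that delays disclosure to the end of data collection, and say to whom each applies.

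**Cost.** Visit 3 exists and the sensor is already in use, so no visit, device or treatment step is added. The recording covers days just before the end of week 4 and not the days after it. The change score for this measure, and any precision that a true activity baseline would have brought, are given up. A 48-hour recording between consent and first stimulation is not proposed, because it would split the baseline visit and delay treatment.
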